5.2 Exclusion Criteria

All participants meeting any of the exclusion criteria at baseline will be excluded from study participation.

- 5.2.1 Within 14 days of known exposure to someone with confirmed SARS CoV2 infection or COVID-19.
- 5.2.2 Acutely ill or febrile 24 hours prior to or at the Screening Visit (Day 0). Fever is defined as a body temperature $\geq 38.0^{\circ}\text{C}/100.4^{\circ}\text{F}$. Participants meeting this criterion may be rescheduled within the relevant window periods. Afebrile participants with minor illnesses can be enrolled at the discretion of the investigator.
- 5.2.3 Participants on the vaccine naïve arms cannot have received any doses of the COVID-19 vaccine.

Participants who have not completed a standard vaccination series due to initiation of vaccination in a foreign location (e.g., single dose of Astra-Zeneca vaccine or a similar situation) may be enrolled after discussion with the principal investigator.

Participants on the booster arms must have received all doses of their initial COVID-19 vaccine (Participants vaccinated with the Janssen vaccine must have received the single dose of that EUA vaccine for COVID19, but all others must have received 2 doses) at least 4 weeks prior to vaccination on protocol. Participants will be allowed to enroll if they have already received booster doses of vaccine prior to enrolling on the protocol at least four weeks prior to vaccination on protocol. In this case, the protocol will administer a single booster dose of vaccination. Documentation will be required.

- 5.2.4 Known diagnosis of chronic pulmonary disease (e.g., chronic obstructive pulmonary disease, asthma) that is not controlled.
- 5.2.5 Chronic cardiovascular disease that is not controlled.
- 5.2.6 Participants with a history of myocarditis (inflammation of the heart) or pericarditis (inflammation of the pericardium)
- 5.2.7 History of anaphylaxis, urticaria, or other significant adverse reaction requiring medical intervention after receipt of a vaccine.
- 5.2.8 Bleeding disorder considered a contraindication to intramuscular (IM) injection or phlebotomy.
- 5.2.9 Participated in an interventional clinical trial with an investigational agent within 28 days prior to the Screening Visit (Day 0) or plans to do so while participating in this study. The site investigator may enroll a participant on the trial earlier than 28 days if enough time has passed to ensure that at least five half-lives have occurred.
- 5.2.10 Prior/Concomitant Therapy
 - Has received prior radiotherapy within 14 days before the first dose of study treatment. Participants must have recovered from all radiation-related toxicities, not require corticosteroids, and not have had radiation pneumonitis. A 7-day washout is permitted for palliative radiation (\leq 2 weeks of radiotherapy) to non-central nervous system (CNS) disease.
 - Has received a live vaccine within 30 days before the first dose of study treatment. Examples of live vaccines include, but are not limited to, the following: measles, mumps, rubella, varicella/zoster (chicken pox), yellow fever, rabies, Bacillus Calmette–Guérin (BCG), and typhoid vaccine. Seasonal influenza vaccines for injection are generally killed virus vaccines and are allowed; however, intranasal influenza vaccines (e.g., FluMist®) are live attenuated vaccines and are not allowed.
- 5.2.11 Has received an inactivated vaccine within 14 days before the first dose of study treatment.
- 5.2.12 Have major surgical procedures within 28 days or non-study-related minor procedures within 7 days before the first dose of study treatment. In all cases, the participant must be sufficiently recovered and stable before treatment administration.
- 5.2.13 History of severe allergic reactions to any components of the study treatment.
- 5.2.14 Has uncontrolled intercurrent illness, including but not limited to, ongoing or active infection, symptomatic congestive heart failure, uncontrolled hypertension, unstable angina pectoris, cardiac arrhythmia, severe or ongoing interstitial lung disease (ILD), serious chronic gastrointestinal conditions associated with diarrhea, or psychiatric illness/social situations that would limit compliance with study requirement, substantially increase risk of incurring AEs, or compromise the ability of the participant to give written informed consent.

- 5.2.15 Active tuberculosis (clinical evaluation that includes clinical history, physical examination and radiographic findings, and tuberculosis testing in line with local practice).
- 5.2.16 History of (non-infectious) pneumonitis that required steroids or has current pneumonitis.
- 5.2.17 Has involvement in the planning and/or conduct of the study.
- 5.2.18 Female who is pregnant or breastfeeding
- 5.2.19 Male or female participant of reproductive potential who are not willing to employ effective birth control from screening to 30 days after the last dose of study treatment.

6 STUDY PROCEDURES

6.1 Planned Study Visits After Enrollment

Participants will undergo study procedures at the time points specified in the protocol Study Calendar ([Appendix E](#)).

6.1.1 Prior to Vaccine Administration

6.1.1.1 Pre-Screening, Day -28 to 0

Potential Participants' information will be pre-screened for study eligibility criteria met. Potential study participants will be provided with information regarding the study and they will be asked if they wish to continue to the Screening Visit Procedures. The initial consent process as well as re-consent, when required, may take place in person or remotely (e.g., via telephone or other site approved remote platforms used in compliance with local policy) per discretion of the designated study investigator and with the agreement of the participant/consent designee(s).

6.1.1.2 Day -28 to -1, Visit 0, Study Screening

Potential participants may be screened for eligibility. All procedures and questions in the medical history that can be conducted by a telephonic visit will be allowed up to a week prior to the study visit. The following activities will be performed at the screening visit:

- Potential participants will be provided with a description of the study (purpose and study procedures). Participants will be asked to read and sign the informed consent form (ICF). The ICF will be signed prior to performing any other screening procedures.
- Eligibility criteria for study entry and receipt of Dose 1 will be reviewed with the participant. Vital signs will be obtained, including temperature, pulse, and blood pressure.
- Height and weight will be obtained.
- Medical history will be reviewed.
- All concomitant medications will be recorded.
- A physical examination will be performed by appropriate study personnel to assess general physical condition.

- Review of acceptable contraceptive methods (male and female participants) and recent menstrual history (female participants only).
- A urine or serum pregnancy test must be performed within one week prior to vaccination for all female participants of childbearing potential.
- Approximately 5-10 ml of venous blood will be collected for serological studies, blood chemistry

6.1.2 Vaccine Administration and Follow-Up for Vaccine-Naïve Cohorts

6.1.2.1 Day 1, Visit 1, Vaccine Dose 1

Unless otherwise indicated, the following baseline evaluations can be performed within 28 days prior the first vaccine administration. The screening evaluations and baseline evaluations may be performed on the same day. Any evaluations required at both timepoints will not need to be duplicated if this occurs.

- Eligibility baseline criteria for study entry and receipt of Dose 1 will be reviewed with the participant.
- Vital signs will be obtained, including weight, temperature, pulse, and blood pressure.
- Medical history will be reviewed to assure continued eligibility.
- All concomitant medications will be reviewed for accuracy and completeness. Any new medications will be recorded and assessed for continuing eligibility.
- A physical examination may be performed, as indicated, based on participant's recent clinical history since the screening visit.
- A urine or serum pregnancy test must be performed within one week prior to vaccination for all female participants of childbearing potential.
- Clinical safety laboratory assessments will be performed by the local laboratory. The results from this blood draw will not be available or reviewed prior to vaccination and will serve as a baseline safety assessment only. Approximately 8-10 ml of venous blood will be collected for serological studies, troponin, blood chemistry. Participants with CLL will also have LDH and Beta-2 microglobulin collected.
- Blood will be collected for baseline immunology assessments (see section [7.3](#)).
- Approximately 1 mL of saliva will be collected for Immunogenicity Evaluation
- An electrocardiogram (ECG) will be performed.
- Participants will receive a single dose of mRNA-1273 vaccine via intramuscular injection in the deltoid muscle of the preferred arm. Following vaccination, participants will be observed in the clinic for at least 15 minutes. The vaccination site will be examined, and any AE/SAEs will be assessed prior to discharge from the clinic.
- Participants will be provided with study related materials to record daily temperature and systemic and local AE/SAEs. Participants will be encouraged to take their temperature around the same time each day. Participants will be instructed on how to measure and record AE/SAEs prior to discharge from the clinic. Participants will be instructed to notify the study center if they develop any severe reactions following vaccination. If the site principal investigator or appropriate sub-investigator deems the reaction severe enough, s/he will give further instructions on the proper course of action, including a return to the clinic for immediate evaluation if appropriate.
- Counseling on avoidance of pregnancy will be conducted.

6.1.2.2 Day 29, Visit 2, Vaccine Dose 2*

*NOTE: If an unavoidable delay requires the participant to receive the second vaccine on a day after day 29, this will be acceptable within a three day timeframe. All subsequent numbering will refer to this visit as the “Day 29, Visit 2” visit and the appropriate blood draws and study procedures will be noted as though the participant received the second dose on schedule, on Day 29. The participant will receive a proof of vaccination card documenting the dates of administration after receiving their second dose of the study drug.

- Vital signs will be obtained, including temperature, pulse, and blood pressure.
- All concomitant medications will be reviewed for accuracy and completeness. Any new medications will be recorded and assessed for continuing eligibility.
- A physical examination may be performed, as indicated, based on participant’s recent clinical history since the screening visit. This is required for participants with CLL and optional for the other cohorts. The medical history will also be reviewed at this time.
- A urine or serum pregnancy test must be performed within one week prior to vaccination for all female participants of childbearing potential.
- Clinical safety laboratory assessments will be performed by the local laboratory. The results from this blood draw will not be available or reviewed prior to vaccination and will serve as a baseline safety assessment only. Approximately 80-100 ml of venous blood will be collected for serological studies, troponin, and blood chemistry. Participants with CLL will also have LDH and Beta-2 microglobulin collected.
- Samples will be collected for immunology/correlative studies (see section [7.3](#)).
- An electrocardiogram will be performed (may be performed up to 2 weeks prior to this visit).
- Participants will receive a single dose of mRNA-1273 vaccine via intramuscular injection in the deltoid muscle. Following vaccination participants will be observed in the clinic for at least 15 minutes. The vaccination site will be examined, and any AE/SAEs will be assessed prior to discharge from the clinic.
- Participants will be provided with study related materials to record daily temperature and systemic and local AE/SAEs. Participants will be encouraged to take their temperature around the same time each day. Participants will be instructed on how to measure and record AE/SAEs prior to discharge from the clinic. Participants will be instructed to notify the study center if they develop any severe reactions following vaccination. If the site principal investigator or appropriate sub-investigator deems the reaction severe enough, s/he will give further instructions on the proper course of action, including a return to the clinic for immediate evaluation if appropriate.
- Participants will be provided with proof of vaccination
- Counseling on avoidance of pregnancy will be conducted.

6.1.2.3 Day 36, Visit 3 (+/- 1 day)

- In-person visit
- Current health status will be reviewed and any changes since the last visit will be noted.
- Samples will be collected for immunology/correlative studies (see section [7.3](#)).
- Solicited AEs/reactogenicity will be reviewed.
- Unsolicited AEs, and SAEs, that have occurred since the last contact will be collected.

6.1.2.4 Day 57, Visit 4 (+/- 7 days)

- In-person visit
- Current health status will be reviewed and any changes since the last visit will be noted.
- Standard antibody testing to assess immune response
- Samples will be collected for immunology/correlative studies (see section [7.3](#)).
- Samples for troponin monitoring will be collected (+/- 2 weeks).
- An electrocardiogram will be performed (+/- 2 weeks).
- Unsolicited AEs, and SAEs, that have occurred since the last contact will be collected.
- Participants with CLL will have the following procedures:
 - Medical history will be reviewed
 - Physical examination
 - LDH and Beta-2 microglobulin will be collected after resumption of BTKi therapy.

6.1.2.5 Day 209 (6 Months), Visit 5 (+/- 28 days)

- In-person visit
- Follow-up interim medical history and vital signs will be completed.
- Unsolicited AEs, and SAEs, that have occurred since the last contact will be collected.
- Samples will be collected for immunology/correlative studies (see section [7.3](#)).
- Standard antibody testing to assess immune response

6.1.2.6 Day 394, Visit 6 (+/- 28 days)

- In-person visit
- Follow-up interim medical history and vital signs will be completed.
- Unsolicited AEs, and SAEs, that have occurred since the last contact will be collected.
- Standard antibody testing to assess immune response
- Samples will be collected for immunology/correlative studies (see section [7.3](#)).
- Participants will be thanked for participating in the study

6.1.3 Vaccine Administration and Follow-Up for Booster Vaccine Cohorts

Participants from the Vaccine-Naïve Cohorts who receive the additional booster will follow-up per the Booster Vaccine Cohort and will follow the below timeline. They will not be required to complete any Vaccine-Naïve Assessments after receiving the booster vaccine. They will become eligible for their respective booster per the Booster Vaccine Cohort 4 weeks after their second vaccination. A physical examination may be performed, as indicated, based on participant's recent clinical history, but for participants transitioning from the Vaccine-Naïve Cohorts, this will not be required. Similarly, baseline labs will not be required for Vaccine-Naïve participants who transition into the Booster Vaccine Cohorts.

Participants who enroll on trial after a previous booster vaccination off-trial will follow the same study calendar, as below, provided at least four weeks have passed from the last booster vaccination.

Similarly, participants who receive an initial booster vaccination from this protocol will be eligible for a second and a third booster vaccination and follow the study the same study calendar as below, provided at least four weeks have passed from the last booster vaccination. The date of

their second booster dose will be considered Day 1. If they receive a third booster dose on protocol, the calendar will be reset, and the date of their third booster will be considered Day 1.

6.1.3.1 Day 1, Visit 1, Booster Vaccine Dose 1

- Unless otherwise indicated, the following baseline evaluations can be performed within 28 days prior to vaccine administration. The screening evaluations and baseline evaluations may be performed on the same day. Any evaluations required at both timepoints will not need to be duplicated if this occurs. As noted above, participants who are transitioning from the Vaccine-Naïve cohorts will not need any baseline labs, as they are already enrolled on the protocol.
- Participants in the BTK inhibitor interruption arm must stop their BTK inhibitor therapy no later than Day -7 and may resume no sooner than Day 15.
- Eligibility baseline criteria for study entry and receipt of Dose 1 will be reviewed with the participant.
- Vital signs will be obtained, including weight, temperature, pulse, and blood pressure.
- Medical history will be reviewed to assure continued eligibility.
- All concomitant medications will be reviewed for accuracy and completeness. Any new medications will be recorded and assessed for continuing eligibility.
- A physical examination may be performed, as indicated, based on participant's recent clinical history since the screening visit.
- A urine or serum pregnancy test must be performed within one week prior to vaccination for all female participants of childbearing potential.
- Clinical safety laboratory assessments will be performed by the local laboratory. The results from this blood draw will not be available or reviewed prior to vaccination and will serve as a baseline safety assessment only. Approximately 8-10 ml of venous blood will be collected for serological studies, troponin, blood chemistry
- Blood will be collected for baseline immunology assessments (see section [7.3](#)).
- An electrocardiogram will be performed
- Approximately 1 mL of saliva will be collected for Immunogenicity Evaluation
- Participants will receive a single dose of mRNA-1273 vaccine via intramuscular injection in the deltoid muscle of the preferred arm. Following vaccination, participants will be observed in the clinic for at least 15 minutes. The vaccination site will be examined, and any AE/SAEs will be assessed prior to discharge from the clinic.
- Participants will be provided with study related materials to record daily temperature and systemic and local AE/SAEs. Participants will be encouraged to take their temperature around the same time each day. Participants will be instructed on how to measure and record AE/SAEs prior to discharge from the clinic. Participants will be instructed to notify the study center if they develop any severe reactions following vaccination. If the site principal investigator or appropriate sub-investigator deems the reaction severe enough, s/he will give further instructions on the proper course of action, including a return to the clinic for immediate evaluation if appropriate.
- Counseling on avoidance of pregnancy will be conducted.

6.1.3.2 Day 8, Visit 2 (REQUIRED FOR CAR T Cell Cohort, OPTIONAL for other cohorts)

- In-person visit
- Current health status will be reviewed and any changes since the last visit will be noted.
- Standard antibody testing to assess immune response
- Samples will be collected for immunology/correlative studies (see section [7.3](#)).
- Solicited AEs/reactogenicity will be reviewed.
- Unsolicited AEs, and SAEs, that have occurred since the last contact will be collected.

6.1.3.3 Day 29, Visit 3

- In-person visit
- Current health status will be reviewed and any changes since the last visit will be noted.
- Standard antibody testing to assess immune response
- Samples will be collected for immunology/correlative studies (see section [7.3](#)).
- Samples for troponin monitoring will be collected (+/- 2 weeks)
- An electrocardiogram will be performed (+/- 2 weeks).
- Solicited AEs/reactogenicity will be reviewed.
- Unsolicited AEs, and SAEs, that have occurred since the last contact will be collected.

6.1.3.4 Day 57, Visit 4 (+/- 7 days)

- In-person visit
- Current health status will be reviewed and any changes since the last visit will be noted.
- Samples will be collected for immunology/correlative studies (see section [7.3](#)).
- Standard antibody testing to assess immune response
- Unsolicited AEs, and SAEs, that have occurred since the last contact will be collected.
- If a participant elects to have a second or third booster vaccination on protocol, the date of administration of this dose will be considered Day 1. The minimum timeframe between booster vaccination doses will be 28 days. Day 57, Day 180, and Day 360 timepoints, if not yet reached on the original booster vaccination on protocol will be timed according to the participant's last vaccination dose.

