3.2 Study Objectives and Endpoints

| Objectives and Endpoints | |
|--|--|
| Primary Objective | Primary Endpoints |
| Safety Objective: To evaluate the safety and reactogenicity of the mRNA-1273 vaccine administered in 2 doses 28 days apart, in participants who have a | Safety Endpoints: 
Solicited local and systemic Adverse Reactions (ARs) through 7 days after each injection. |

| Objectives and Endpoints | |
|--|---|
| Primary Objective | Primary Endpoints |
| hematological malignancy and are immunosuppressed due to their disease and/or treatment, or receiving a PD-1/PDL-1 inhibitor for treatment of a solid tumor for participants who are vaccine- naïve. To evaluate the safety and reactogenicity of booster doses of mRNA-1273 vaccine administered to participants with cancer who have previously received an mRNA or alternative vaccine regimen | 
Unsolicited AEs through 28 days after each injection.SAEs throughout the entire study period.Vital sign measurements and physical examination findings. |
| Immunogenicity Objective: To assess the immunogenicity of mRNA-1273 in participants with cancer, as assessed by the titer or level of specific binding antibody (bAb) | Immunogenicity Endpoints: 
Titer or level of specific binding antibody (bAb), in participantsTiter or level of SARS-CoV-2-specific binding antibody (bAb) measured by ELISA on Day 1, Day 29, Day 36, Day 57 Day 209 and Day 394 for participants on Vaccine-Naïve CohortsTiter or level of SARS-CoV-2-specific binding antibody (bAb) measured by ELISA on Day 1, Day 29, Day 180, Day 360 for participants on Booster Vaccine Cohorts |

| Secondary Objective | Secondary Endpoints |
|---|--|
| To evaluate the immunogenicity of the mRNA-1273 vaccine administered, as assessed by the titer or level of neutralizing antibody (nAb). | For Vaccine-Naïve Cohorts: 
Titer or level of SARS-CoV-2-specific neutralizing antibody (nAb) on Day 1, Day 29, Day 36, Day 57, Day 209, and Day 394Seroconversion due to vaccination on Day 29, Day 36, Day 57, Day 209, and Day 394 measured as:
For subjects with no detectable antibody titer (< |

| Secondary Objective | Secondary Endpoints |
|---------------------|---|

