6.1.3.6 Day 360, Visit 6 (+/- 28 days)

- In-person visit
- Follow-up interim medical history and vital signs will be completed.
- Unsolicited AEs, and SAEs, that have occurred since the last contact will be collected.
- Samples will be collected for immunology/correlative studies (see section [7.3](#)).
- Standard antibody testing to assess immune response
- Participants will be thanked for participating in the study
- If a participant elects to have a second or third booster vaccination on protocol, the date of administration of this dose will be considered Day 1. The minimum timeframe between booster vaccination doses will be 28 days. Day 360 timepoint, if not yet reached on the original booster vaccination on protocol will be timed according to the participant's last vaccination dose.

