- d) Participants on the booster vaccine cohorts will receive an injection of mRNA-1273 into muscle on Day 1 and will be followed through 12 months post vaccination (Day 360). Participants will receive proof of vaccination.
- e) In-person clinical visits will occur at screening, and on Baseline/Days 1 (may occur on same day), 29, 57, 180 and at 360. These visits at clinic will take approximately 4-6 hours.
- f) Participants with CLL will have LDH and Beta-2 microglobulin drawn on Day 57. Participants in other cohorts will not have safety labs drawn at this visit.
- g) If a participant elects to have a second or third booster vaccination on protocol, the date of administration of the last dose will be considered Day 1. The minimum timeframe between booster vaccination doses will be 28 days. Day 57, Day 180, and Day 360 timepoints, if not yet reached on the original booster vaccination on protocol will be timed according to the participant's last vaccination dose.
- h) Collection of all AEs from the participant, solicited and unsolicited, will occur during the period from study product administration on Day 1 through 28 days after the last vaccination. Adverse events that are serious need to be recorded after 28 days following the last vaccine, only if they are related to the study intervention.
- i) The ECG may be performed up to 2 weeks before or 2 weeks after Day 29.

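### After a second or third on-study booster, section 6.1.3 restarts the visit calendar, but 6.1.3.4 to 6.1.3.6 and Appendix G note g re-time only outstanding Day 57, 180 and 360 visits; read literally, a later booster has no scheduled Day 29 visit

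*Combined protocol and SAP*

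**What the plan says.** - **Section 6.1.3.** Participants boosted on protocol may have a second and third booster on the same calendar, "provided at least four weeks have passed from the last booster vaccination". The date of "their second booster dose will be considered Day 1"; for a third, "the calendar will be reset, and the date of their third booster will be considered Day 1".
- **Sections 6.1.3.4 to 6.1.3.6.** Each repeats that the later dose is Day 1 and that doses are at least 28 days apart, then adds a limit. Under the Day 57 visit: "Day 57, Day 180, and Day 360 timepoints, if not yet reached on the original booster vaccination on protocol will be timed" from the last dose. Under Day 180, only Days 180 and 360 are named. Under Day 360: "Day 360 timepoint, if not yet reached on the original booster vaccination on protocol will be timed according to" the last dose.
- **Appendix G, note g.** The last dose is Day 1, followed by the same limit: "Day 57, Day 180, and Day 360 timepoints, if not yet reached on the original booster vaccination".
- **Section 3.2.** Primary safety endpoints are solicited reactions for 7 days after each injection and "Unsolicited AEs through 28 days after each injection". Day 29 is a primary binding-antibody timepoint for the booster cohorts.
- **Booster visit content (6.1.3.2 to 6.1.3.6).** Solicited events are reviewed at Day 8 (required only in the CAR T cohort) and Day 29. Day 29 has the only scheduled post-dose troponin and ECG. Days 57, 180 and 360 list unsolicited events and SAEs, but no solicited review.

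**The concern.** The two sets of instructions give different schedules for the same participant. Under a full restart, every on-study booster is followed by a Day 29 visit. Under the limiting sentence, only visits still outstanding from the first on-study booster move to the new clock, and Day 29 is not among them.

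Two features of the wording favour the limiting interpretation. If everything restarted, the condition that a timepoint has not yet been reached would do no work. The list of named visits also shrinks from three to two to one as follow-up advances, which fits completed visits being dropped and not repeated.

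Booster safety is a primary objective and up to three boosters are allowed. Sites following different sections would see participants at different times after a later booster and collect different data. On the limiting interpretation, the Day 29 antibody summary would have no scheduled sample for those doses.

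**Working it through.** The plan gives no figure to reproduce, so the check is visit-day arithmetic.

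**Inputs.** Minimum interval of 28 days (6.1.3.4, note g). Visit windows from Appendix G: Day 8 ± 1, Day 29 ± 3, Day 57 ± 7, Day 180 ± 28, Day 360 ± 28. Safety windows of 7 and 28 days (3.2).

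**Formula.** Days after dose = visit day − 1, plus or minus the window.

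**Earliest later booster.** Day 1 + 28 = Day 29. Day 8 has always passed by then, and Day 29 has normally been reached.

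**Full restart (6.1.3).** Day 8 falls 7 ± 1 = 6-8 days after the dose. Day 29 falls 28 ± 3 = 25-31 days after it.

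**Limiting sentence taken literally:**

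| Later booster given | First scheduled visit | Days after dose | Days after the 28-day window closes |
|---|---|---|---|
| Days 29-56 | Day 57 | 56 ± 7 = 49-63 | 21-35 |
| After the Day 57 visit | Day 180 | 179 ± 28 = 151-207 | 123-179 |
| After the Day 180 visit | Day 360 | 359 ± 28 = 331-387 | 303-359 |
| At or after Day 360 | none | none | none |

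The row boundaries assume visits on their nominal days. A Day 57 visit made early, from Day 50, moves the first boundary accordingly.

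**Cardiac checks.** The halting rule in 8.9.1 covers myocarditis or pericarditis within 6 weeks, that is 42 days. The earliest visit on the literal interpretation is at 49 days, and the Day 57 visit includes neither troponin nor ECG.

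**Length of follow-up under a full restart.** A booster given on Day 360 followed by the whole calendar takes 359 + 359 = 718 days from the first on-study booster, about 718 / 30.4 = 23.6 months. The Protocol Summary gives about 14 months per participant and 16 months for the study.

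**The case against.** The strongest reply is that the passages can be reconciled. All of them call the later dose Day 1. The limiting sentence may only say that visits outstanding from the first booster move to the new clock, so that two calendars do not run together. Days 8 and 29 would then be missing from the list because nothing is left to move. No passage says that Day 29 is not repeated. This stands to the extent that the fault is an ambiguity and not an express rule against a Day 29 visit. But the plan does not state this reconciliation, and note g puts the limiting wording in the calendar itself.

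A reader might infer that the primary safety windows of later boosters go unobserved. The documents do not support that. Section 7.1.4 requires an 8-day memory aid after each vaccination and its review with the participant. Section 8.1.2 requires solicited events through 7 days after each vaccination, and 8.3 requires all events through 28 days after the last. Later visits ask about unsolicited events since the last contact. Section 6.3 asks for effort towards a safety visit about 28 days after the last dose.

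These rules close the gap only in part:

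- The only visit that 7.1.4 names for memory-aid review is Day 8. The aids are not source documents and are destroyed once staff have completed the source by interview.
- The day labels in 7.1.4 and 8.1.2 (Days 1-8 and 29-36) reach a later booster only if Day 1 is reset.
- The visit in 6.3 applies before removal from study, not routinely after each booster.

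It is also fair to say that Day 8 is optional outside the CAR T cohort even after a first booster. The main loss is therefore Day 29.

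**Conclusion.** The inconsistency holds and should be resolved. On the literal interpretation, no scheduled visit falls within 7 or 28 days of a later booster. The first comes at 49-63 days at best and not at all for a booster at or after Day 360. No listed visit reviews solicited events for that dose, and the Day 29 binding-antibody sample, troponin and ECG are unscheduled. What is lost is scheduled, in-window assessment; the duty to collect adverse events remains.

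Two further inferences go too far. One is that sites would record few or no events, so that repeat boosting would look falsely well tolerated. Nothing in the plan shows this, given the per-dose collection rules. The other is that most injections are affected. Later boosters could be at most 2 × 80 + 2 × 140 = 440 of 80 × 5 + 140 × 3 = 820 injections (53.7%), but only if all 220 participants took three on-study boosters. Uptake is not stated, section 5.2.3 gives a single protocol booster to those already boosted elsewhere, and 6.1.3 puts them on the full calendar. The figure is a ceiling, not an estimate.

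The sizes rest on the literal interpretation, nominal visit days and the Appendix G windows.

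**What to change.** Reconcile 6.1.3.4, 6.1.3.5, 6.1.3.6 and Appendix G note g with the visit rule in 6.1.3:

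- State that the Day 29 assessments already in the calendar, and Day 8 where it is required, are timed from every on-study booster, even if the visit of the same name was completed after an earlier dose.
- State which of the Day 57, 180 and 360 visits repeat after a later booster.
- State in 11.4.2.1 which Day 1 is the baseline for the geometric mean fold rise when a participant has more than one on-study booster.
- Reconcile follow-up after a late booster, including one elected at the Day 360 visit, with the participation and study durations in the Protocol Summary.

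The cost is a wording amendment in four places plus these clarifications, at least one extra visit per later booster compared with the literal interpretation, and possibly longer follow-up. No dose or dosing interval changes.
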